#### 7.2.1 Exclusion criteria related to study methodology

- E 01. Age <55 years at Screening.
- E 02. Body mass index (BMI)  $\leq 20$  or  $>45$  kg/m^2 at Screening or BW that exceeds the weight limits of the DXA scanner.
- E 03. Use of systemic glucocorticoids (excluding topical, intra-articular, or ophthalmic application, nasal spray or inhaled forms) for more than 10 consecutive days within 90 days prior to Screening.
- E 04. Use of weight loss medications within 12 weeks or weight change of 5 kg or more during the 12 weeks prior to Screening.
- E 05. Likelihood of requiring treatment during the study period with drugs not permitted by the study protocol (eg, long-term systemic glucocorticoids) and refusing or unable to take alternative treatment.
- E 06. Patient who has previously been randomized in any clinical trial of sotagliflozin/LX4211.
- E 07. Patients with severe anemia, severe CV disease (including congestive heart failure New York Heart Association IV), respiratory, hepatic, neurological, psychiatric, or active malignant tumor or other major systemic disease or patients with short life expectancy that, according to the Investigator, will preclude their safe participation in this study or will make implementation of the protocol or interpretation of the study results difficult.

- E 08. Current diagnosis of chronic hepatitis and/or other clinically active liver disease.
- E 09. Known presence of factors that interfere with the central laboratory HbA1c measurement (eg, genetic Hb variants) compromising the reliability of HbA1c assessment or medical conditions that affect interpretation of HbA1c results (eg, blood transfusion or severe blood loss in the last 3 months prior to randomization, any condition that shortens erythrocyte survival).
- E 10. History of drug or alcohol abuse within 6 months prior to Screening.
- E 11. Patient is an employee of the Sponsor, or is the Investigator or any Sub-investigator, research assistant, pharmacist, study coordinator, other staff or relative thereof directly involved in conducting the study.
- E 12. Patient who has taken other investigational drugs or prohibited therapy for this study within 12 weeks or 5 half-lives from screening or randomization, whichever is longer.

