### 10.1.1.1 Screening Phase

The Screening Phase will be up to 2 weeks in duration and includes Visit 1 (Week -4) only. The Screening Phase must be long enough to collect the data to establish whether the patient satisfies the inclusion/exclusion criteria.

Patients will undergo Screening assessments at Visit 1 (Week -4) following signing of the ICF. Patients who meet the inclusion criteria as noted in [Section 7.1](#) and meet no exclusion criteria as noted in [Section 7.2](#) will be randomized at Visit 3 (Day 1).

The IRT will be contacted at Visit 1 for notification of Screening Visit and to obtain the patient number.

In cases where original screen failure was due to reasons expected to change at rescreening and based upon the Investigator's clinical judgment, the patient can be rescreened once prior to entering the Run-in Phase of this study. In these cases, a patient will need to sign a new ICF, be registered as a rescreened in IRT, and assigned a new patient number in IRT (first Screening Visit is to be registered as screen failure in IRT), and complete Screening Visit procedures and assessments again.

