#### 10.1.1.1.1 Screening Visit, Visit 1 (Week -4)

The following procedures/assessments will be performed at Visit 1 (Week -4):

- Obtain informed consent:
  - The patient will receive verbal information concerning the aims and methods of the study, its constraints and risks, and the study duration. Written information will be provided to the patient. Written informed consent must be signed by the patient and Investigator prior to any investigations.
  - 
- IRT notification (allocation of ID, registration of Screening).
- Assessment of inclusion/exclusion criteria.
- Collection of demographic data (age, gender, race, and ethnic origin).
- Assessment of the patient's medical and surgical history, including history, treatment and complications (eye, kidney, history of smoking/tobacco use, history of alcohol, and history of amputation events, etc) of T2D.
- Concomitant medication and medication history, including any prior medications for T2D.
- Measurement of BW and height.
- Complete physical examination including vital signs (SBP and DBP, HR, temperature, and respiratory rate) (see [Appendix C](#) for details).
- The following laboratory testing (by the central laboratory):
  - Serum 25-hydroxyvitamin D.

- HbA1c.
- Serum FSH and estradiol (for documentation of menopausal status).
- Clinical chemistry (including amylase, lipase) and hematology.
- AEs/SAEs/AESI/EOSI and hypoglycemia (if any) are reported.
- Urinalysis (dipstick and microscopy).
- Patients will be instructed to return to the site in the fasting state for Visit 3 (Week 0).

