2 STATISTICAL AND ANALYTICAL PROCEDURES

2.1 ANALYSIS ENDPOINTS

2.1.1 Demographic and baseline characteristics

The baseline value (with the exception of serum creatinine and eGFR) is defined as the last available value before the first dose of double-blind investigational medicinal product (IMP) or the last available value prior to randomization for patients who were randomized but never exposed to IMP.

For serum creatinine and eGFR, the baseline value is defined as average of all values before the first dose of double-blind IMP for patients randomized and exposed or before randomization for patients who were randomized but never exposed to IMP.

All baseline safety and efficacy parameters are presented along with the summary statistics in the safety and efficacy sections ([Section 2.4.5](#) and [Section 2.4.4](#)).

Demographic characteristics

Demographic characteristics to be summarized are:

- Age (years) derived as: Year of informed consent - Year of birth.
- Age categories (≥ 55 to < 65 , ≥ 65 to < 75 , ≥ 75 years).
- Gender (Male, Female).
- Race (White, Black or African American, Asian, American Indian or Alaska native, Native Hawaiian or other pacific islander, Multiple, Unknown).
- Ethnicity (Hispanic or Latino, Not Hispanic or Latino, Unknown).
- HbA1c (%) at screening visit.
- Randomization strata of HbA1c ($\leq 8.5\%$, $> 8.5\%$) at screening visit (data from IRT).
- Randomization strata of Gender (Male, Female) (data from IRT).
- Mean SBP at screening visit.
- Mean SBP categories (< 130 mmHg, ≥ 130 mmHg).
- Baseline body mass index (BMI) (kg/m^2) derived as: $(\text{Weight in kg})/(\text{Height in meters})^2$.
- Baseline BMI categories (< 30 , ≥ 30 kg/m^2).
- Baseline BMD T-score (lumbar spine, total hip, or femoral neck).
- Mean serum 25-hydroxyvitamin D at screening visit.
- Country.

Disease characteristics at screening or Baseline

Disease history includes:

- Duration of diabetes (years) derived as: (Date of informed consent – Date of diagnosis of diabetes + 1)/365.25.
- Duration of diabetes categories: (<10, ≥10 years).
- Age at diagnosis of diabetes (years) derived as: Year of diagnosis of diabetes – Year of Birth.
- Prior antidiabetic medication (in monotherapy or combination):
 - No antidiabetic therapy,
 - Insulin (alone or with OADs),
 - SU and/or glinide (alone or with other OADs),
 - Metformin (alone or with OADs other than SU and glinide),
 - OADs other than SU, glinide and metformin,
 - GLP-1 receptor agonist.

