The tipping point analysis will be performed on the ITT population. The tipping point analyses will be performed only if the corresponding primary or secondary endpoints (change from Baseline to Week 26 in HbA1c comparing sotagliflozin 400 mg vs placebo, or comparing sotagliflozin 200 mg vs placebo) is statistically significant at $\alpha = 0.05$ (2-sided).

In addition to the tipping point analyses, if the retrieved dropout imputation is applied to the primary analysis, the analysis based on the washout imputation method (ie, the backup imputation method) will be presented as a sensitivity analysis.

Assessment of treatment effect by subgroup

Descriptive analyses will be performed on the primary endpoint to summarize the treatment effects across subgroups defined by the following Baseline or Screening factors:

- Race (White, Black or African American, Asian, Other) (any race groups with fewer than 5 patients may be combined with “Other” category as appropriate).
- Ethnicity (Hispanic, Not Hispanic).
- Age group (<65, ≥ 65 years),
- Gender (Male, Female).
- Baseline BMI level (<30, ≥ 30 kg/m²).
- Baseline HbA1c ($\leq 8.5\%$, $> 8.5\%$).
- Baseline mean SBP (<130 mmHg, ≥ 130 mmHg).
- Baseline eGFR (≥ 30 to <60 mL/min/1.73m² [Moderate decrease in GFR], ≥ 60 to <90 mL/min/1.73m² [Mild decrease in GFR], and ≥ 90 mL/min/1.73m² [Normal]).
- Duration of diabetes (<10, ≥ 10 years).
- Prior antidiabetic medication [No antidiabetic therapy, Insulin (alone or with other antihyperglycemic agents), SU and/or glinide (alone or with other non-insulin antihyperglycemic agents), other (non-insulin antihyperglycemic agents except SU, and glinide)].
- Country.

The treatment effects (sotagliflozin 400 mg and sotagliflozin 200mg, respectively, versus placebo) across the subgroups defined for each of these factors will be estimated for the change from Baseline to Week 26 in HbA1c in the ITT population, and using the same MI method as applied to the primary analysis.

The ANCOVA model will include treatment groups (sotagliflozin 400 mg, sotagliflozin 200 mg, placebo), randomization stratum of HbA1c ($\leq 8.5\%$, $> 8.5\%$), randomization stratum of sex

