This sensitivity analysis will serve as the primary analysis at any timepoint if the number of patients who prematurely discontinue the IMP before the post-Baseline visit (Week 26, Week 52, or Week 104) with the visit data is not sufficient to perform a retrieved dropout analysis.

Descriptive analyses will be performed on the key safety endpoints to summarize the treatment effects across subgroups defined by the following baseline or screening factors:

- Age group (< 65 years, ≥ 65 years).
- Duration of T2D (< 10 years, ≥ 10 years).
- Sex (male, female).
- Baseline BMI level (< 25 ; 25 to < 35 ; ≥ 35 kg/m²).
- Baseline eGFR (< 45 ; 45 to < 60 ; ≥ 60 mL/min/1.73 m²).

The treatment effects (sotagliflozin 400 mg and sotagliflozin 200 mg versus placebo respectively) across the subgroups defined for each of these factors will be estimated for the percent change from Baseline to Week 26, Week 52, and Week 104 in BMD in the safety population, and using the same MI method as applied to each of the key safety endpoints, respectively.

The ANCOVA model will include treatment groups (sotagliflozin 400 mg, sotagliflozin 200 mg, placebo), randomization stratum of HbA1c ($\leq 8.5\%$, $> 8.5\%$), randomization stratum of sex (male, female), subgroup factor, treatment-by-subgroup factor, and country as fixed effects, and baseline BMD value as covariate.

The adjusted estimates of treatment mean differences with SE and 95% CIs will be provided as appropriate across the subgroups (comparing each sotagliflozin group vs placebo group) with SE and 95% CIs will be provided as appropriate across the subgroups. A forest plot of the results will also be presented.

In the case that the subgroup factor is the sex only the subgroup factor (as a single factor and/or an interaction term) will be included in the model in order to avoid the issue of collinearity in the analysis. The corresponding strata factor will not be included in the model.

Summary statistics (including number, mean, median, Q1, Q3, standard deviation, standard error, minimum and maximum) of BMD (lumbar spine, total hip, femoral neck) (baseline value, observed post-Baseline values, observed changes from Baseline and observed percent change from Baseline) will be provided at Week 26, Week 52 and Week 104 by treatment group. Graphical presentations will be used to examine trends over time using mean (\pm SE), mean change

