2.5.3 Missing data

For categorical variables, patients with missing data are not included in calculations of percentages unless otherwise specified. When relevant, the number of patients with missing data is presented.

Derived variables will be considered missing if any of the original variables required to calculate them are missing. For example, if either a baseline assessment or an endpoint assessment is missing for a particular patient, then change from Baseline at endpoint will be missing. Depending upon the assessment, analyses may not include all patients in the analysis population, because certain patients in the intended population may have missing data.

Incomplete date of first administration of double-blind IMP

Date/time of first administration is the first non-missing start date/time of double-blind IMP

completed in the e-CRF “First dose IMP” module.

For patients who are randomized and dispensed a double-blind treatment kit but who are lost to follow-up just after Visit 3 (eg. only the treatment kit number is reported in the e-CRF “Exposure - treatment period” module without any dose information), the date of first administration will be imputed using the date of randomization. When a patient is randomized but not exposed, “Not taken” should be ticked in the e-CRF “First dose IMP” module.

Handling of computation of treatment duration if IMP end of treatment date is missing

For the calculation of the treatment duration, the date of the last dose of IMP is equal to the date of last administration reported on the end-of-treatment case report form page. If this date is missing, the exposure duration should be left as missing.

The last dose intake should be clearly identified in the case report form and should not be approximated by the last returned package date.

Handling of medication missing/partial dates

No imputation of medication start/end dates or times will be performed. If a medication date or time is missing or partially missing and it cannot be determined whether it was taken prior or concomitantly, it will be considered a prior, concomitant, and posttreatment medication.

Handling of adverse events/hypoglycemia with missing or partial date/time of onset

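### Deriving age as consent year minus birth year puts roughly 40–65% of patients one year above their completed age and moves about half of the 64-year-olds into the ≥65 groups

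*SAP*

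**What the plan says.** SAP 2.1.1 defines age by subtracting calendar years: "Age (years) derived as: Year of informed consent - Year of birth". The SAP gives no other derivation of age at entry. The same section then sets three age categories with cuts at 65 and 75.

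The 65-year cut returns in four places:

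- HbA1c (SAP 2.4.4.1): "Descriptive analyses will be performed on the primary endpoint to summarize the treatment effects across subgroups defined by the following Baseline or Screening factors", with age among them.
- BMD (SAP 2.4.5.1): "Descriptive analyses will be performed on the key safety endpoints to summarize the treatment effects across subgroups", again including age.
- Severe or documented symptomatic hypoglycemia (SAP 2.4.5.2).
- Common TEAEs (SAP 2.4.5.3).

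The 75-year cut appears only in the categories of 2.1.1.

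The protocol already has an age at Screening. Its list of Visit 1 procedures (10.1.1.1.1) contains the item "Collection of demographic data (age, gender, race, and ethnic origin", and exclusion E 01 reads "Age <55 years at Screening". Consent belongs to the same visit: "Patients will undergo Screening assessments at Visit 1 (Week -4) following signing of the ICF" (10.1.1.1).

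**The concern.** A difference of calendar years ignores month and day. A patient born in November and consenting in May has not yet had that year's birthday, so the formula adds a year that has not been completed. The error is either 0 or +1 year. Because it is never negative, patients cross a cut-off in one direction only: a 64-year-old can enter the ≥65 group, but a 65-year-old cannot leave it.

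The trial enrols patients aged 55 or older and presents bone results by age. The age table and the membership of the ≥65 groups should therefore follow the ordinary meaning of age. As written, the label ≥65 covers some patients who were 64 when they entered, although the protocol collects their age at that visit.

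**Working it through.** The plan states no figure for this point. Its one relevant calculation is the primary power: 120 per arm, difference 0.6 and SD 1.2 give 97.2%, which matches the stated 97%. Age does not enter it.

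**Inputs from the documents.** The derivation (SAP 2.1.1), 360 patients in total (SAP 1.1), and first enrolment on 14 March 2018 (SAP 1.5). The end of enrolment and the age distribution are not given and are assumed below.

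**1. Form of the error.** Derived age = completed age + 1 if the birthday falls after the consent date in that calendar year; otherwise derived age = completed age.

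**2. Share overstated.** With birthdays uniform over the year, a consent on day k leaves a fraction (365 − k)/365 of birthdays still to come. Averaging over evenly spread consent days (14 March is day 73):

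| Consent period | Calculation | Share one year too high |
|---|---|---|
| Full calendar year | (364 + 0)/730 | 49.9% |
| 14 Mar to 30 Jun 2018 | (292 + 184)/730 | 65% |
| 14 Mar to 30 Sep 2018 | (292 + 92)/730 | 53% |
| 14 Mar to 31 Dec 2018 | (292 + 0)/730 | 40% |
| 14 Mar 2018 to 13 Mar 2019 | (293 × 0.40 + 72 × 0.90)/365 | 50% |
| 14 Mar 2018 to 30 Jun 2019 | (293 × 0.40 + 181 × 0.751)/474 | 53% |

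**3. Patients moved across 65.** Moved = 360 × share aged 64 × share with the birthday still to come. Three age distributions were assumed and simulated with 400,000 patients each, with consents over a full year:

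| Assumed age distribution | Share aged 64 | Moved to ≥65, of 360 | Moved to ≥75, of 360 |
|---|---|---|---|
| Uniform 55–80 | 4.0% | 7.2 | 7.2 |
| Normal, mean 65, SD 6, cut at 55 | 7.0% | 12.7 | 3.5 |
| 55 + exponential, mean 9 | 3.9% | 6.9 | 2.3 |

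By hand, the first row is 360 × 0.040 × 0.50 = 7.2. The range is about 7–13 patients; dividing by three arms gives 2–4 per arm. With the extreme shares from step 2, the outer limits are 360 × 0.0387 × 0.40 = 5.6 and 360 × 0.0705 × 0.65 = 16.5. No simulated patient moved from ≥65 to <65.

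**4. Weight in the ≥65 group.** The true ≥65 shares are 15/25 = 60% (216 patients) for the uniform, 0.5/0.952 = 52.5% (189) for the normal and e^(−10/9) = 32.9% (118.5) for the exponential. The moved patients then form 7.2/223.2 = 3.2%, 12.7/201.7 = 6.3% and 6.9/125.4 = 5.5% of the derived group. Suppose the moved patients had no HbA1c effect, the others had the planned −0.6, and the moved share were equal across arms. The subgroup estimate would then shift by at most 0.063 × 0.6 ≈ 0.04 percentage points.

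**5. Mean error.** It is +0.5 year against completed age and about 0 against exact decimal age.

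**The case against.** The strongest reply is that almost nothing depends on this. Age is neither a stratification factor nor a model term. The age subgroups are descriptive. The rule uses pre-randomization data and treats all arms alike, so it favours no arm within a subgroup. All of this stands, and step 4 confirms that the effect on a subgroup estimate is very small.

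It can also be said that the formula is unbiased for exact age and that the moved patients are nearly 65. This too is correct. With uniform dates, the time r (in years) to their birthday has density 2(1 − r). Its mean is one third of a year, or four months, and a proportion 1 − 0.5² = 75% turn 65 within half a year of consent. All do so in the calendar year of consent, hence before Week 52. But subgroups labelled <65 and ≥65 are read in completed years at entry, and against that reading the error runs one way.

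A third reply is that the formula may be all the data allow. The SAP also uses only birth year for age at diagnosis of diabetes, which would fit a database that holds no full date of birth. The documents do not settle this. They do list age as an item collected at Visit 1, but the eCRF is not among them, so a separately recorded age is likely but not shown. The fix therefore needs a fallback.

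Finally, the protocol and SAP do not conflict over when age is taken: consent and age collection belong to the same visit. The fault lies in ignoring month and day.

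**Conclusion.** The point holds as a minor one. The stated rule gives values one year above completed age for about 50% of patients if consents span a full year, or about 40–65% depending on the enrolment calendar. Roughly 7–13 of 360 patients aged 64 are placed in the ≥65 group and about 2–7 aged 74 in the ≥75 category. These counts rest on uniform birthdays, evenly spread consents and assumed age distributions. Only the baseline age table and the four descriptive age splits are affected.

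A reader might infer more, but the documents do not support it:

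- **That the rule hides breaches of E 01.** Eligibility is assessed at Screening, not through this summary variable. SAP 2.2.1 treats randomizing an ineligible patient as an irregularity to be documented. No patient truly aged 55 or older is derived as younger.
- **That fracture or volume-depletion results in older patients are distorted.** SAP 2.4.5.3 summarizes these events of special interest by treatment group, with no age split.
- **That eGFR is wrong.** The central laboratory calculates it (Protocol 9.1.4.5, SAP 2.1.3). SAP 2.5.1 prints a formula with an age term, but nothing ties that term to the derived age. One year at 64 would change eGFR by (65/64)^(−0.203) − 1 ≈ −0.3%.
- **That the neighbouring variable, "Duration of diabetes (years) derived as" a difference of full dates, loses patients who know only the year of diagnosis.** SAP 2.5.3 says "Derived variables will be considered missing if any of the original variables required to calculate them are missing", but does not say that a partial date counts as missing, and the documents give no frequency of such dates.

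**What to change.** In SAP 2.1.1, replace the year-difference formula with age in completed years as collected at the Screening Visit (Protocol 10.1.1.1.1). Use that one variable for the baseline age categories and for the age subgroups in 2.4.4.1, 2.4.5.1, 2.4.5.2 and 2.4.5.3. Keep the year difference only where no Screening age is recorded, report how many patients that concerns, and state the limitation that it can exceed completed age by one year.

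The cost is one SAP line and a small programming change. If the database holds the age recorded at Visit 1, no new data are needed; this should be confirmed against the eCRF first. The same rule should apply to the Week 26 and final analyses, so that no patient changes age group between the two.

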2.1.2 Prior or concomitant medications

All medications taken within 3 months before the screening visit (any time for prior SGLT2) and until the end of the study are to be reported in the electronic case report form (e-CRF) pages.

All medications will be coded using the World Health Organization-Drug Dictionary (WHO-DD) using the version currently in effect at Covance at the time of database lock.

- Prior medications are those the patient used prior to first investigational medicinal product (IMP) intake. Prior medications can be discontinued before first administration or can be ongoing during treatment phase.
- Concomitant medications are any treatments received by the patient concomitantly to the IMP, from the first administration of double-blind IMP to the date of last administration of double-blind IMP + 10 days. A given medication can be classified both as a prior medication and as a concomitant medication.
- Posttreatment medications are those the patient took in the period running from the 11th day after the last administration of double-blind IMP up to the end of the study.

Background therapy consisting of a stable antidiabetes regimen in monotherapy or combination therapy (including oral antidiabetes medications, insulin, or GLP-1 agonists) for more than 12 weeks are considered as noninvestigational medicinal products (NIMP).

Any technical details related to computation, dates imputation for missing dates are described in [Section 2.5](#).

